9.3 Efficacy – Derived Variables

This section defines how the secondary efficacy variables will be derived.

The length of the subject's Treatment Period will be calculated as (see [Table 3](#)):

$$\text{EoT Visit date} - \text{Day 1 Visit or first IP date (if available)} + 1$$

For subjects without EoT visit date, the last available visit or event date will be used (whichever is later).

To transform the daily rate to monthly or yearly rates, the daily rate will be multiplied by 30.4375 or 365.25, respectively.

To calculate the time-normalized number of HAE attacks for historical data use the entry on the eCRF 'HAE History' "Number of HAE attacks during the 6 months before Screening" or in the case of prophylactic HAE therapy within the 6 months before the Screening Visit "If

yes, Number of HAE attacks within 6 months before initiation of prophylactic therapy". The length of the period in the denominator will be 6 and 0.5 for the monthly and yearly rate, respectively.

The derivation of the different secondary efficacy variables are provided below.

Time-normalized number of HAE attacks per day:

$$\frac{\text{Number of HAE attacks}}{\text{Length of subject's Treatment Period (days)}}$$

Time-normalized number of HAE attacks treated with on-demand treatment per day:

$$\frac{\text{Number of HAE attacks treated with on-demand treatment during Treatment Period}}{\text{Length of subject's Treatment Period (days)}}$$

Percentage reduction in time-normalized number of HAE attack:

$$100 * \left(1 - \frac{\text{time-normalized number of HAE attacks per month during the Treatment Period}}{\text{time-normalized number of HAE attacks per month from historical data}} \right)$$

Maximum attack-free time:

First, the following will be calculated:

- (1) For subjects with at least 1 HAE attack calculate the time to the first attack following [Section 7.2.2](#).
- (2) After the last HAE attack a subject experienced, the remaining time will be censored at the EoT Visit and calculated as EoT Visit date - end date of the last attack. For subjects without EoT visit date, the last available visit or event date will be used (whichever is later).
- (3) The time between subsequent HAE attacks will be calculated as start date/time of the following HAE attack - end date/time of the preceding HAE attack.

Maximum attack-free time will be derived as follows:

Subjects without attacks: censored at the EoT Visit date and equal to the length of the Treatment Period.

Subjects with only 1 attack: the maximum of the time to the first attack (1) and the remaining time until EoT Visit (2). If the maximum is the remaining time until EoT maximum attack-free time will be considered censored.

Subjects with multiple attacks: the maximum attack-free time will be the maximum of the time to the first attack (1), the time(s) between subsequent attacks (3), and the remaining time (2). If the maximum is the remaining time until EoT maximum attack-free time will be considered censored.

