### Number of Subjects

The target sample size for this study is approximately 20 subjects to ensure that at least 15 subjects complete 12 months of treatment.

**Note:** Subjects are considered “enrolled” in the study when they, or their legally authorized representative, has agreed to participate in a clinical study after completing the informed consent process and Screening. Potential subjects who are screened to determine their eligibility but fail Screening or do not meet all eligibility criteria are not considered enrolled.

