The number of HAE attacks experienced by each subject, as well as the timing of (recurrent) HAE attacks, will be assessed. Different time-to-event analyses will be performed (eg, time to first HAE attack and maximum attack-free time). The maximum attack-free time is defined as the maximum time a subject was attack-free between all subsequent HAE attacks, calculated as start date / time of the following HAE attack - end date / time of the preceding HAE attack. Subjects with no HAE attack, no second HAE attack, no third HAE attack, etc, will be censored at the End of Treatment Visit. The maximum attack-free time for subjects with no attacks is equal to their length of treatment.

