3.4 Determination of the Sample Size

No formal sample size calculation is made, and the sample size is not based on formal statistical considerations. This study will enroll a prespecified number of subjects as agreed with health authorities. See [Section 5.2](#) for definition of "enrolled".

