Efficacy: Second 6 Months	Month 6 (Day 181) Visit Date + 1 day	Month 12 (Day 361) EoT Visit Date. If the EoT Visit of a subject is delayed by more than the treatment time window relative to the last IP administration, EoT Visit date will be set to last IP administration + 30 days or + 60 days for Q1M or Q2M, respectively.	End Date – Start Date + 1
Safety: First 3 Months	Date of first IP	EoT date if subjects discontinued or date of first IP + 90 if subjects is ongoing	End Date – Start Date + 1
Safety: Second 3 Months	End Date of previous 3- Months' Time Window + 1	EoT date if subjects discontinued or start date + 90 if subjects is ongoing	End Date – Start Date + 1
Safety: Third 3 Months	End Date of previous 3- Months' Time Window + 1	EoT date if subjects discontinued or start date + 90 if subjects is ongoing	End Date – Start Date + 1

Time Window	Start Date	End Date	Duration
Safety: Fourth 3 Months	End Date of previous 3-Months' Time Window + 1	EoT date if subjects discontinued or start date + 90 if subjects is ongoing	End Date – Start Date + 1
Safety: Fifth 3 Months (if applicable)	End Date of previous 3-Months' Time Window + 1	EoT date if subjects discontinued or start date + 90 if subjects is ongoing	End Date – Start Date + 1
...			

Note:

The first day of the Treatment Period may occur on the same day as the Screening Visit for subjects meeting the eligibility criteria for the study. In this case, the duration of the Screening Period is 0.

The Follow-up Visit is mandatory in this study unless a subject chooses to continue to receive CSL312 (and meet the criteria to participate in a post-study access program) or another prophylactic treatment. For these subjects, the Follow-up Period is not applicable.

The length of the month in the 3-Months' Safety time windows is set to 30 days.

8 Study Population

Unless otherwise stated, all tables and listings in this section will be presented by dosing regimen (100 mg Q2M and 100 mg Q1M) and overall.

Subjects who turn 6 years of age during the study will remain on their dosing regimen from study start and will be analyzed for the age group at their date of consent.

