- Time from end of first HAE attack to start of second HAE attack (only for subjects experiencing at least one attack which ends within the Treatment Period). Subjects without a second attack will be censored at the EoT Visit date (or last available visit or event date if no EoT Visit date is available).
- Time from end of second to start of third HAE attack (only for subjects experiencing a second attack which ends within the Treatment Period). Subjects without a third attack will be censored at the EoT Visit date (or last available visit or event date if no EoT Visit date is available).

The following will be derived and analyzed for all subjects in the Enrolled Analysis Set:

- Maximum attack-free time.

The maximum attack-free time is defined as the maximum time a subject was attack-free between all subsequent HAE attacks the subject experienced. The maximum attack-free time for subjects without attacks is equal to the length of the subject's efficacy evaluation period. For the derivation see [Section 9.3](#).

For derivation of the times-to-event see [Section 7.2.2](#). Time-to-events will be derived within the Treatment/Efficacy Evaluation Period (see [Table 2](#)).

For each of the events above the following will be presented:

- The number and percentage of subjects who do not experience the event (not applicable for the maximum attack-free time).
- The median time, the 75% and 25% percentile times of subjects being event-free / having no second / having no third HAE attack, respectively. The median, 25%, and 75% percentile times are defined as the times for which the Kaplan-Meier estimates for the time-to-event functions equal 0.5, 0.75, and 0.25, respectively.
If the time-to-event function is horizontal at 75%, 50% or 25%, the median or

percentiles will be calculated as the average of the two values between which the time-to-event function is horizontal.

- The minimum and maximum times to the event.

Kaplan-Meier curves with two-sided 95% CI will be plotted showing the percentage of subjects being event-free at certain times.

For time between first and second/time between second and third attack the percentages will be calculated using the number of subjects not having the second/third attack at that time as the numerator and the number of subjects having at least one/two event(s) as the denominator.

The corresponding life tables will also be presented.

A by-subject listing will be provided for

- Time to first attack (in days),

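### Maximum attack-free time is known over each child's own evaluation period, but Kaplan-Meier with informative censoring overstates its median or leaves it not reached at low attack rates

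*SAP*

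**What the plan says.** SAP Section 9.2.1.5 lists maximum attack-free time beside time to first attack and the times between successive attacks. For all of them it asks for "The median time, the 75% and 25% percentile times of subjects being event-free", read from Kaplan-Meier estimates, together with Kaplan-Meier curves and 95% intervals. The only exemption for maximum attack-free time is the count of children without the event; the median, quartiles and curve still apply.

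SAP Section 9.3 takes the largest of three kinds of gap: time to first attack, times between attacks, and time from the last attack to the End of Treatment (EoT) Visit. Attack-free children are censored at the EoT Visit. For children with attacks, "If the maximum is the remaining time until EoT maximum attack-free time will be considered censored".

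Both documents also treat the variable as a bounded quantity with a definite value. SAP Section 9.2.1.5 says "Time-to-events will be derived within the Treatment/Efficacy Evaluation Period" and "The maximum attack-free time for subjects without attacks is equal to the length of the subject's efficacy evaluation period". Protocol Section 9.4.2.2.1 says "The maximum attack-free time for subjects with no attacks is equal to their length of treatment". That protocol section also names the variable as an example of a time-to-event analysis and censors children without a first, second or third attack at the EoT Visit. It does not mention Kaplan-Meier, and it does not say that a final gap is censored when it is the longest.

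**The concern.** Kaplan-Meier is meant for a time that has not been fully seen, with censoring unrelated to how long that time would have been. Neither condition fits here. The longest gap within a child's evaluation period is known when the period ends. The children flagged as censored are disproportionately those with few or no attacks, who have the longest gaps.

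The rule is also asymmetric. A child whose longest gap ended in an attack counts as an event, although a longer gap could have followed after EoT. If the target is the maximum within the period, nothing is censored by reaching EoT. If the target is a maximum without time limit, no child's value is final. The curve and its 95% band therefore estimate no defined quantity.

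At stake is one descriptive efficacy result, which would look better than the data or be reported as not reached when a value exists.

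**Working it through.** The plan states no figure for this variable, and its sample size is not calculated (SAP Section 3.4: "No formal sample size calculation is made, and the sample size is not based on formal statistical considerations"), so there is no figure to reproduce.

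**Inputs from the documents.** Size: "approximately 20 subjects to ensure that at least 15 subjects complete 12 months of treatment" (Protocol synopsis). Follow-up: Day 1 to "Month 12 (Day 361) EoT Visit Date" (SAP Table 3), which is 361 days. Month: 30.4375 days (SAP Section 7.2.2). For orientation only, Protocol Section 2.1.1.2.2 reports phase 2 means of 0.05 and 0.35 attacks per month at 200 mg and 600 mg in adults.

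**Assumptions.** Attack rates of 0.05 to 1 per month, Poisson attacks lasting 3 days, at least 24 hours between attacks, no dropout in the base case, 1,500 simulated trials per scenario.

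**Step 1: who is censored.** With k attacks there are k+1 gaps. If they are exchangeable, the last is the longest with probability 1/(k+1). The expected maximum, as a share of the period, is H(k+1)/(k+1), where H(n) = 1 + 1/2 + ... + 1/n.

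| k | P(censored) | Expected maximum |
|---|---|---|
| 0 | 100% | 100% |
| 1 | 50% | 1.5/2 = 75% |
| 2 | 33% | 1.833/3 = 61% |
| 3 | 25% | 2.083/4 = 52% |

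Both columns fall together, which is the informative censoring.

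**Step 2: share censored overall.** For Poisson attacks with mean m = rate × 361/30.4375, the expected value of 1/(k+1) is (1 − exp(−m))/m. At 0.1 per month, m = 1.186 and (1 − 0.305)/1.186 = 59%. At 0.2 per month, m = 2.372 and (1 − 0.093)/2.372 = 38%. The simulation gives the same shares.

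**Step 3: a small example.** Take hypothetical values of 100, 150c, 200, 250c and 361c days (c = censored). Kaplan-Meier falls to 4/5 = 0.80 at 100 days and to 0.80 × 2/3 = 0.53 at 200 days, then stays there. The median is not reached. The plain median is 200 days.

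**Step 4: simulation of the SAP rule, 20 children.**

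| Rate/month | Censored | Mean maximum, censored vs uncensored (days) | Plain median (days) | Kaplan-Meier median not reached | Mean excess when reached (days) |
|---|---|---|---|---|---|
| 0.05 | 75% | 334 vs 250 | 361 | 97% | +28 |
| 0.1 | 59% | 307 vs 233 | 279 | 52% | +45 |
| 0.2 | 38% | 255 vs 201 | 208 | 1% | +31 |
| 0.35 | 23% | 198 vs 164 | 159 | 0.1% | +12 |
| 1.0 | 8% | 96 vs 90 | 84 | 0% | +2 |

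The excess is paired: Kaplan-Meier minus plain median in the same trial, over trials where the Kaplan-Meier median exists. Runs with 2-day attacks agree: not reached in 49% to 52% of trials and otherwise +45 to +46 days at 0.1 per month, about +30 days at 0.2, and 1 to 2 days at 1 per month.

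**Step 5: sensitivity.** If rates vary strongly between children (gamma, shape 0.5), the median is not reached in 95% of trials at 0.1 per month, 68% at 0.2, 35% at 0.35 and 3% at 1.0; the excess at 1.0 is then +15 days. With 25% dropout and a common rate, the excess is +64 days at 0.1 and +40 days at 0.2.

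**Direction.** A Kaplan-Meier curve never lies below the empirical curve of the same values, so the shift is upward. A lower Kaplan-Meier median appeared in fewer than 1% of trials, only through the handling of a curve exactly flat at 0.5.

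**The case against.** Several points on the other side stand.

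- **The protocol calls this a time-to-event analysis.** The SAP is following Protocol Section 9.4.2.2.1 in spirit, and SAP Section 4 declares no changes. A reader might infer that the SAP departed from the protocol, or that the correction is mere wording. The documents support neither. What the SAP adds is Kaplan-Meier and the rule on the final gap.
- **Known does not mean observed for 12 months.** A reader might infer that every child's value is fully observed. That holds only over the child's own evaluation period. A child who leaves after Day 30 stays in the efficacy summaries (SAP Section 9), with a period that ends at the last visit or event. With 5 of 20 leaving uniformly between Day 31 and Day 361 (assumed, 2-day attacks), the plain median falls from 283 to 251 days at 0.1 per month and from 210 to 193 days at 0.2. The plain median therefore has its own downward bias, and part of the larger excess under dropout in Step 5 reflects this.
- **The value does not itself trigger censoring.** A reader might infer that it does. The rule looks at the position of the longest gap. At a fixed attack count, the simulated mean maximum is almost the same whether censored or not: 269.9 vs 270.2 days with one attack, 218.3 vs 218.0 with two (0.1 per month, 2-day attacks). The dependence runs through the number of attacks, which is enough to make the censoring informative.
- **Little is lost at the extremes.** At 1 per month with a common rate the two medians nearly agree. When more than half the children are attack-free, the plain median is itself the ceiling of about 361 days.
- **The raw values remain visible.** The by-subject listing gives each value and its censoring flag, so a reader could recover the plain median of about 20 children. The summary table would still show the distorted one.

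**Conclusion.** The concern holds with these limits. As written, the SAP gives a Kaplan-Meier median for maximum attack-free time that is too long, or not reached, whenever on-treatment attack rates are low. With 20 children and 361 days, the median is not reached in about half of trials at 0.1 attacks per month and is otherwise about 45 days too long. The excess is about 30 days at 0.2 per month and 1 to 2 days at 1 per month under a common rate. These sizes rest on assumed rates, attack lengths and Poisson timing, because the documents give no on-treatment rate for children.

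A reader might infer that a secondary or primary result is at risk. It is not: the variable is absent from the secondary endpoint lists in both documents, it appears among the supplementary analyses in the SAP, and no test or decision uses it. The censoring rules for time to first, second and third attack are not part of this point. The correction is worth making because it is cheap and the stated rule yields a figure with no clear meaning.

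**What to change.** 1. In SAP Sections 9.2.1.5 and 9.3, take maximum attack-free time out of the Kaplan-Meier analyses and delete its censoring rules. Keep the derivation of the value.
2. Summarise the derived value by regimen and overall: n, median, Q1, Q3, minimum and maximum. Add the number of children who were attack-free and the number whose longest gap was still running at EoT.
3. Show length of observation alongside, and present the summary both for all children and for those completing 12 months.
4. Record the change in SAP Section 4, because the protocol lists the variable among its time-to-event analyses.
5. Keep Kaplan-Meier for time to first attack.

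The cost is revised SAP wording, an entry in Section 4 and a changed output with a second version for completers. The downsides are a less favourable figure, a small departure from the protocol's wording, and a plain median that shortens with dropout unless the completers' summary is read beside it.

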9.4 Multiple Comparisons and Multiplicity

The study is single-arm open-label. Comparisons are not planned, and multiplicity is not applicable.

9.5 Missing Data and Imputation

Efficacy endpoints will be only missing for analysis if the subject discontinued the study within 30 days after the Day 1 Visit date. Missing data will not be imputed.

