### **9.4.2. Efficacy Analyses**

The efficacy endpoints will not be calculated if the subject's observation time for the Treatment Period is less than 30 days, ie, the subject discontinued within 30 days after the Day 1 Visit or the date of the first investigational product administration, if available.

The efficacy endpoints will also be assessed over time for 6-month (ie, 182-day) time windows, with the first window starting at Visit Day 1.

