7.1 Missing Data

Missing data occurs when any requested data are not provided, leading to blank fields on the collection instrument. These data will be indicated using a "blank" in subject listing displays. Answers such as "Not applicable" and "Not evaluable" are not considered to be missing data and should be displayed as such.

The primary safety endpoint is TEAEs and will not be missing. The monitoring of reported AEs is performed throughout the study. If inconsistencies are detected, queries will be generated. If a subject did not report TEAEs, the number of TEAEs will be 0.

As only descriptive statistics will be presented for all PK parameters (primary PK endpoints), missing data will not be imputed.

Missing efficacy data will not be imputed, as there is no formal statistical analysis being done. All subjects who drop out within the first 30 days of the treatment period will be regarded as missing for all efficacy analyses.

The details of handling missing data are presented in the corresponding sections of this SAP for the respective analyses (e.g., efficacy analyses, safety analyses).

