Subjects may discontinue treatment but remain in the study until the Follow-up Visit. These subjects will be reported for treatment discontinuation, but not for study discontinuation. Other subjects may discontinue treatment and discontinue the study during the treatment period. These subjects will be reported for treatment and study discontinuation. Subjects who choose not to continue to receive CSL312 or another prophylactic treatment after this study may complete treatment and discontinue from the study during follow-up. These subjects will be reported for study discontinuation but not for treatment discontinuation. Subjects who choose to continue to receive CSL312 or another prophylactic treatment after this study will be reported as study completer if they completed treatment and not entered the Follow-up Period provided they answered the corresponding question in the eCRF ("Did the subject complete the study?") with "Yes".

Reasons for study and study treatment discontinuation will be presented in the order they are displayed in the eCRF.

The following by-subject listings will be provided:

- Disposition including date of informed consent, date of eligibility, date of first and last IP administration, EoT Visit date, Follow-up Visit date, reason for treatment discontinuation and/or study discontinuation.
- Assignment to analysis sets (included in Analysis Set: Screened Analysis Set [yes, no], Enrolled Analysis Set [yes, no], PP Analysis Set [yes, no], Safety Analysis Set [yes, no], PK Analysis Set [yes, no], PD Analysis Set [yes, no], reason(s) for exclusion from any analysis set).

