8.5 Study Population - Derived Variables

Derivation of BMI at Baseline

BMI will be calculated using the following formula:

$$\text{BMI (kg/m}^2\text{)} = \text{Weight (kg)} / [\text{Height (m)}]^2$$

using the height measured at Screening and the weight measured at Baseline (see [Section 7.2.3](#)). If weight at Baseline is not available, the BMI will be missing.

BMI at later visits will be derived based on the most recent assessment of height and weight at the respective visit.

9 Efficacy Analyses

The primary objective of the study is to evaluate the safety and PK of SC administration of CSL312 in the prophylactic treatment of pediatric subjects with C1-INH HAE. Thus, the primary endpoints of the study are a safety and PK endpoint and not an efficacy endpoint. Please see [Section 10.2.1](#) and [Section 11](#) for a description of the primary safety and PK endpoints, respectively, and corresponding analysis.

Subjects who turn 6 years of age during the study will remain on their dosing regimen from study start and will be analyzed in the age group according to the subject's age at the time of consent.

The efficacy endpoints will not be included in any efficacy summary if the subject's duration for the Treatment Period is less than 30 days, i.e., the subject discontinued within 30 days after the Day 1 Visit date or the date of first IP, if available. The reason why an endpoint is not included will be provided in the by-subject listing.

The efficacy endpoints will also be assessed over time for 6-months' time windows, with the first window starting at the Day 1 Visit date or the date of first IP, if available. Only subjects who completed the entire time window (i.e., completed Visit Month 6 and Visit Month 12,

respectively) – allowing for visit windows as per Schedule of Assessment in the protocol – will be included in the analysis of this time window.

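### SAP 9.5 ties the 30-day efficacy exclusion to leaving the study, SAP 9 and Protocol 9.4.2 tie it to Treatment Period length, and the exclusion needlessly reaches Kaplan-Meier time to first attack

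*SAP*

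**What the plan says.** The 30-day exclusion appears in three forms.

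- **Duration.** The opening text of SAP section 9 says: "The efficacy endpoints will not be included in any efficacy summary if the subject's duration for the Treatment Period is less than 30 days". The same sentence explains this as the subject having discontinued within 30 days of the Day 1 Visit or first dose. Protocol 9.4.2 uses the same test ("observation time for the Treatment Period is less than 30 days") and the same explanation.
- **Drop-out.** SAP 7.1 says: "All subjects who drop out within the first 30 days of the treatment period will be regarded as missing for all efficacy analyses". Protocol 9.4.7 agrees. Neither says whether the drop-out is from treatment or from the study.
- **Study discontinuation.** SAP 9.5 says: "Efficacy endpoints will be only missing for analysis if the subject discontinued the study within 30 days after the Day 1 Visit date". It counts from the Day 1 Visit only, with no mention of the first dose.

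The plan treats stopping treatment and leaving the study as separate events. The note in SAP 8.1 says: "Subjects may discontinue treatment but remain in the study until the Follow-up Visit". Protocol 7.1 likewise keeps children who stop the product in the study. SAP Table 3 ends the Treatment Period at the End of Treatment (EoT) Visit or, if there is none, at the last available visit or event.

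For time to first attack, SAP 9.2.1.5 has its own censoring rule: attack-free subjects are censored at the EoT Visit, or at the last visit or event. It does not mention the 30-day exclusion. For maximum attack-free time it says: "The following will be derived and analyzed for all subjects in the Enrolled Analysis Set".

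**The concern.** The word only in SAP 9.5 makes study discontinuation the sole reason for a missing endpoint, so it cannot simply be added to the duration test. Two programmers following different sections could build different analysis populations. The study is open-label, so an unresolved choice would be made with outcomes visible.

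The second issue is scope. A minimum duration makes sense for a rate with a very short denominator. Kaplan-Meier estimation does not need one, because a child observed for a short time contributes that time and is then censored. Excluding the child discards observed data, including any attack.

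**Working it through.** The plan has no figure of its own to reproduce. The check applies each rule to the same hypothetical child and then sizes the effect.

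**Inputs from the documents**
- About 20 children, at least 15 completers (Protocol 4.1, SAP 3).
- Duration = End − Start + 1 (SAP Table 3).
- Monthly rate = attacks / days × 30.4375 (Protocol 9.4.2.2.1.1, SAP 9.3).

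**Assumed for illustration**
- One child has the first dose on Day 1, an attack on Day 10 and an EoT Visit on Day 20.
- 12 of the other 19 children are attack-free.

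**1. Keep or drop.** Duration = 20 − 1 + 1 = 20 days, below 30, so SAP 9 and Protocol 9.4.2 drop the child. If the child stays in the study, SAP 9.5 keeps the child. If the child also leaves the study on Day 20, every rule drops the child.

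**2. Day counts at the edge.** The table takes Day 1 as the first-dose date. It reads drop-out, and the explanation inside the SAP 9 sentence, as stopping treatment.

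| Days after first dose | Duration | Duration below 30 | Drop-out in first 30 days | Within 30 days after | SAP 9.5, stays in study | SAP 9.5, leaves study |
|---|---|---|---|---|---|---|
| 19 | 20 | drop | drop | drop | keep | drop |
| 28 | 29 | drop | drop | drop | keep | drop |
| 29 | 30 | keep | drop | drop | keep | drop |
| 30 | 31 | keep | keep | drop | keep | drop |
| 31 | 32 | keep | keep | keep | keep | keep |

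The phrase "duration for the Treatment Period is less than 30 days, i.e., the subject discontinued within 30 days" therefore joins two tests that disagree at durations of 30 and 31 days. This can arise from the plan's own rule. A once-monthly child with one dose and a late EoT Visit has the end date reset to first dose + 30, so the duration is 31. The duration test keeps that child. The explanation drops the child if the reset date counts as discontinuation.

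**3. Kaplan-Meier time to first attack.** Assume no other attack by Day 31.
- Child kept: 1 − 1/20 = 95% attack-free at Day 31.
- Child dropped: 100%.
- With two or three such children: 90% or 85% if kept, 100% if dropped.

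The direction depends on the attack. From the day of the dropped child's attack, the curve is higher without that child. Before that day it can be marginally lower if someone else attacked first. With another attack on Day 5, the curve before Day 10 is 19/20 = 95.0% kept and 18/19 = 94.7% dropped. From Day 10 it is 18/20 = 90.0% kept and 18/19 = 94.7% dropped. Dropping an early leaver who had no attack never raises the curve.

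**4. Proportion without an attack.**
- Kept: 12/20 = 60.0% (Wilson 95% CI 38.7 to 78.1).
- Dropped: 12/19 = 63.2% (41.0 to 80.9).

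**5. Mean rate.** The child's rate is 1/20 × 30.4375 = 1.52 per month. The shift in the mean from including the child is (1.52 − mean of the other 19)/20.
- If the other 19 have no attacks: 1.52/20 = 0.076, the upper bound for this child.
- If 7 of the 19 have 0.1 per month: mean of the others = 0.7/19 = 0.037, so the shift is (1.52 − 0.037)/20 = 0.074.

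**6. Median rate.** With 12 zeros among 20 or among 19, the middle values are zero. The median is 0 either way.

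**7. How many children.** If the 5 non-completers that the target allows (20 − 15) were spread evenly over 360 days, 5 × 30/360 = 0.42 would leave in the first 30 days. Only some of these would also have an early EoT Visit and stay in the study.

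**The case against.** The strongest reply is that SAP 9.5 is one loose sentence. Protocol 9.4.2, Protocol 9.4.7, SAP 7.1 and SAP 9 all refer to the Treatment Period, and SAP section 4 says no change from the protocol analyses is planned. The conflict is also hard to reach. Protocol 7.2 asks for EoT assessments when a subject withdraws from the study, whereas Protocol 7.1 prescribes no early EoT Visit for a child who only stops the product. The first scheduled visit after Day 1 is Day 31 (ages 6 to 11) or Day 61 (ages 2 to 5). Without an EoT Visit the Treatment Period runs to the last visit or event, usually past 30 days, and the duration test and SAP 9.5 both keep the child. All of this stands as a limit on frequency. It does not remove the contradiction, since the documents allow an early EoT Visit with continued participation.

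On Kaplan-Meier, the exclusion is prespecified in the protocol, time to event is supplementary, and listings and subject profiles show every attack and the reason for each omission. That gives transparency, but it does not correct the curve.

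The sentence on maximum attack-free time is weak evidence of a further contradiction. Its reference to all enrolled subjects may only contrast with the preceding items, which are limited to children with one or two attacks.

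A reader might infer more than the documents support:
- That early attacks in general vanish from the analysis. Only excluded children's attacks do; first-month attacks in the others count, and there is a separate Day 1 to Day 31 analysis.
- That early leavers are mostly treatment failures. Nothing in the documents says so.
- That 0.076 is large because the protocol quotes a mean of 0.05 for adults on 200 mg. That arm had 8 subjects and is no benchmark here.

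**Conclusion.** The point holds in a limited form. SAP 9.5 and SAP 9 give opposite results for a child who stops treatment, has an EoT Visit before Day 30 and remains in the study, and the day counts disagree by one or two days. Applying the exclusion to time to first attack also discards observed attacks without need, and the curve is too high from each such attack onward.

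It would be wrong to read this as early failures generally being kept or dropped at will. A child who leaves both treatment and study by about Day 29 is dropped under every rule, and the conflict group may be empty. The endpoints are secondary or supplementary and descriptive, so no error rate or power is affected. The median, which is of primary interest, does not move in the illustration. The sizes (at most 0.076 per month on the mean, 63% against 60% attack-free, 100% against 95% on the curve at Day 31) rest on assumed attack and stopping patterns in 20 children. The 0.4 early leavers rest on even drop-out and treat the allowance of 5 as the expected number. This should be corrected before database lock, but it does not threaten the study's primary conclusions.

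**What to change.** - In SAP 7.1, 9 and 9.5, state one rule: time-normalized rates and percentage reduction are not summarized when the Table 3 Treatment Period duration is under 30 days. Delete the study-discontinuation wording in 9.5 and the explanatory clause in section 9 that gives a different day count.
- Do not apply the exclusion to Kaplan-Meier time to first attack or to total attack counts. Analyse these in the Enrolled Analysis Set, which includes enrolled but untreated children, and censor at the end of each subject's own Treatment Period.
- The attack-free category in SAP 9.2.1.4 is a percentage reduction and stays under the exclusion. Footnote its denominator where it differs from the time-to-event table.
- Declare the narrower scope in SAP section 4 as a change from Protocol 9.4.2 and 9.4.7.

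No new data are needed. The cost is a declared departure from the protocol, so this is more than a wording edit, and a possibly slightly less favourable attack-free estimate.
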